1.0 Objectives / Specific Aims

- Objective: Determine the optimal dose of IV N-acetylcysteine (NAC) to produce opioid reduction following spine surgery and estimate the difference in opioid consumption between placebo and the selected optimal dose.
- The primary outcome will be 12-hour postoperative opioid consumption.
- The secondary outcomes will be 6-hour postoperative opioid consumption.
- Other exploratory outcomes will include intraoperative opioid consumption, postoperative anesthesia care unit (PACU) opioid consumption cumulative, non-opioid analgesic administration, postoperative opioid consumption at additional time points, and VAS pain scores. Patient demographic data, surgical data (procedure, operative duration), preoperative opioid consumption, time to hospital discharge will also be collected.

2.0 Background

As the opioid epidemic has gained notoriety, opioid sparing strategies have garnered more interest to provide analgesia without addictive potential, opioid related side effects, and elevated costs. Anesthesiologists and surgeons face the challenge of avoiding long term opioid use while still attempting to control the discomfort associated with invasive procedure. Additionally, postoperative opioids can lead to abuse by patients or others.¹

N-acetylcysteine (NAC) has been an established drug since the 1960s. It is on the World Health Organization's List of 40 Essential Medicines)^a and is FDA approved. NAC is a precursor to the amino acid L-cysteine and the antioxidant glutathione (GSH),² shown to promote homeostatic glutamate regulation by astrocytes. The sulphydryl group (–SH) within the NAC molecule directly scavenges reactive oxygen species (ROS),³ modulates the redox state of the N-methyl-D-aspartate (NMDA) and α -amino-3-hydroxy-5-methyl-4-isoxazolepropionic acid (AMPA) receptors (neurotransmitter effect),⁴ and inhibits the nuclear factor kappa-light-chain-enhancer of activated B cells (NF- κ B) to modulate cytokine synthesis (anti/pro-inflammatory effect).⁵

NAC is probably best known as the treatment for hepatotoxicity from acetaminophen toxicity.^{6b} However, NAC has also been utilized to treat psychiatric disorders (e.g., schizophrenia, obsessive compulsive disorders, addiction, compulsion, anxiety), neurodegenerative disease symptoms (e.g., Alzheimer's disease, Parkinson's disease),

^a World Health Organization. WHO Model List of Essential Medicines: 20th List. March 2017. Available online: http://www.who.int/medicines/publications/essentialmedicines/20th_EML2017_FINAL_amendedAug2017.pdf?ua=1 (accessed February 24, 2020).

^b FDA. Acetadote (acetylcysteine) Injection Package Insert. Available online: https://www.accessdata.fda.gov/drugsatfda_docs/nda/2004/21-539_Acetadote.cfm (accessed on 22 February 24, 2020).

fertility, oral ulcers, chronic pain, hyperglycemia-induced oxidative damage, traumatic brain injury, and numerous other conditions.⁷⁻¹⁶ There are also case reports of NAC helping with improving neurological status in patients comatose from carbon monoxide poisoning.¹⁷ In the perioperative period, NAC has been primarily studied for its anti-inflammatory properties¹⁸ and was noted to reduce the incidence of atrial fibrillation after coronary artery bypass graft surgery.¹⁹ Although NAC has been used in outpatient studies for patients with chronic pain associated with sickle cell anemia²⁰ and diabetic neuropathy,^{14,21} we are not aware of any studies examining NAC to enhance perioperative analgesia and decrease opioid administration.

3.0 Intervention to be studied

This study will involve administration of IV NAC or placebo (0.45% NaCl or 0.9% NaCl) in the perioperative period to patients scheduled for elective spine surgery and observation of postoperative opioid consumption. Our hypothesis is that NAC will reduce postoperative opioid consumption. This study will also examine the optimal dose of NAC to reduce opioid consumption.

NAC has a long history of safe administration and is frequently administered to critically ill patients.^{6,17,19}

Medication information: NAC is FDA approved for multiple indications including an antidote to poisoning caused by acetaminophen overdose and prevention of acute hepatic injury.^b It has been utilized to treat critically ill patients for over 60 years. It is generally well tolerated and has an excellent safety profile. Due to this excellent safety profile and with the approved dosing, this study will utilize NAC doses equal to the loading dose for acetaminophen treatment (150 mg/kg) or less (50 or 100 mg/kg).

Mechanism: NAC exerts its therapeutic effect through several mechanisms. NAC repletes glutathione reserves by providing cysteine, which is an essential precursor in glutathione production. NAC by itself also binds to toxic metabolites and scavenges free radicals. It also increases oxygen delivery to tissues, by increasing mitochondrial ATP production, and altering the microvascular tone to increase blood flow and oxygen delivery to the liver and other vital organs.

4.0 Study Endpoints

- The primary outcome will be 12-hour postoperative opioid consumption.
- The secondary outcome will be 6-hour postoperative opioid pain score.
- Other exploratory outcomes will include intraoperative opioid consumption, postoperative anesthesia care unit (PACU) opioid consumption cumulative, non-opioid analgesic administration, postoperative opioid consumption at additional time points, and VAS pain scores at additional time points.
- Other collected data will include patient demographic data, surgical data (procedure, operative duration), preoperative opioid consumption, time to hospital discharge.

5.0 Inclusion and Exclusion Criteria/ Study Population

- **Inclusion**
 - Undergoing elective spine surgery involving 4 levels or less of the thoracic, lumbar, or sacral spine.
 - 18 years of age and older.
- **Exclusion**
 - Less than 40kg in weight.
 - Unable to provide written, informed consent.
 - History of an adverse or anaphylactoid reaction to acetylcysteine.
 - Active asthma, wheezing, or using inhaled bronchodilators.
 - Pregnant Women
 - Known blood clotting deficiency
 - Insulin dependent diabetes

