9.0 Consent Process

- Regardless of the preoperative location, the study team will present to the subject with risks and benefits of the study and the study medication (NAC). Subjects may provide written consent at that time or choose to consider the study until the day of surgery. Potential participants will be given time to read the consent and ask questions. Consent will be obtained from subjects by an IRB approved CITI certified study team member that has been trained on the protocol. Written consent will be completed once all questions are answered and exclusion and inclusion verified. Copies of all documents will be provided to the patients.

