15.0 Risks to Subjects

- IV NAC can cause rate related anaphylactoid reactions in 0.2-18% of patients.^{22,23c} Most of the anaphylactoid reactions are mild (6%) or moderate (10%) with severe reactions (i.e., bronchospasm and hypotension) rare at 1% or less. Bronchospasm more commonly occurs in patients with pre-existing reactive airway diseases, like asthma. Bronchodilating agents are effective in treating these patients. To minimize this risk, patients with asthma, wheezing, or prescribed bronchodilators will be excluded from the study. Similarly, patients with a history of a prior anaphylactoid reactions to acetylcysteine will also be excluded.

If an anaphylactoid events occurs, patients will be treated as described by FDA guidelines.^b IV NAC will be stopped immediately and the patient treated with antihistamine medication (e.g., diphenhydramine) and IV fluids if required. Vasopressors are not typically necessary. NAC therapy may be restarted at a slower rate after resolution of any possible reaction. However, if an anaphylactoid reaction or

similar symptoms return upon reinitiating NAC treatment or increases in severity, IV NAC will be discontinued. Additionally, all possible medication reactions will be reported to the Anesthesia DSMB and MUSC IRB.

There is also a risk of loss of confidentiality.

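### Section 15 claims a broader asthma and bronchodilator exclusion than the Section 5 eligibility list applies, so patients with quiescent asthma can be enrolled despite the stated safeguard

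*Protocol*

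**What the plan says.** Protocol Section 5.0 lists the exclusion as "Active asthma, wheezing, or using inhaled bronchodilators". It does not define what makes asthma active.

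Protocol Section 15.0 gives the reason for the exclusion: "Bronchospasm more commonly occurs in patients with pre-existing reactive airway diseases, like asthma". It then states the control: "To minimize this risk, patients with asthma, wheezing, or prescribed bronchodilators will be excluded from the study".

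Section 9.0 ties eligibility to the consent step: "Written consent will be completed once all questions are answered and exclusion and inclusion verified". It does not say which wording is to be checked. The SAP does not deal with eligibility.

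**The concern.** Both sentences describe the same safety exclusion, yet only wheezing is treated identically. Section 5 limits asthma to the active form; Section 15 does not. Section 5 requires that a bronchodilator be in use and be inhaled. Section 15 requires only that one be prescribed, by any route.

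What is at stake is whether the protocol delivers the protection it describes. Anyone who judges the bronchospasm risk from Section 15 would believe that all patients with asthma are kept out. A screener working from Section 5 would let in a patient whose asthma is quiescent. Section 15's own reason refers to pre-existing reactive airway disease in general, so that patient belongs to the group it worries about.

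**Working it through.** The plan has no figure to reproduce on this point. The check compares the two texts as logical rules.

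**Inputs**

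- Section 5.0: excluded if asthma is active, or the patient wheezes, or an inhaled bronchodilator is in use.
- Section 15.0: said to be excluded if the patient has any asthma, or wheezes, or has any bronchodilator prescribed.
- I read *using* as current use and *prescribed* as covering any route, used or not.

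**Side by side** (the first four rows have neither wheeze nor active asthma)

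| Patient | Section 5 list | Section 15 statement | Conflict |
|---|---|---|---|
| Quiescent asthma, no bronchodilator | not excluded | said to be excluded | yes |
| No asthma, inhaled bronchodilator prescribed but unused | not excluded | said to be excluded | yes |
| No asthma, non-inhaled bronchodilator prescribed | not excluded | said to be excluded | yes |
| No asthma, inhaled bronchodilator in use without prescription | excluded | not mentioned | no |
| Active asthma or wheeze | excluded | said to be excluded | no |

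**Full cross-classification.** Take asthma as none, inactive or active (3), wheeze as no or yes (2), and seven bronchodilator states: none, or inhaled or non-inhaled, each prescribed and used, prescribed only, or used only. That gives 3 × 2 × 7 = 42 combinations.

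- The two texts, each treated as a complete rule, differ in 9 combinations.
- One of the 9 is the fourth row of the table, where Section 15 is merely silent. That leaves 9 − 1 = 8 in which Section 5 admits a patient whom Section 15 says is excluded.
- Of these 8, 5 involve inactive asthma and 3 involve a prescription in a patient without asthma.
- All 8 reduce to the three conflicting types in the table, or to combinations or subdivisions of them.

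These are logical combinations, not patients, so 8 of 42 is not a proportion of anyone enrolled.

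**After the fix.** Under the union rule (any asthma, or wheeze, or any prescribed bronchodilator, or an inhaled one in use), all 8 combinations are excluded and 0 conflicts remain. The patient in the fourth row stays excluded, as under Section 5 now.

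**The case against.** The strongest reply is that Section 5 is the eligibility list and Section 15 a loose summary of it. There is support for this. Section 15 also shortens the prior-reaction criterion: it says "patients with a history of a prior anaphylactoid reactions to acetylcysteine will also be excluded", where Section 5 has the wider "History of an adverse or anaphylactoid reaction to acetylcysteine". On that reading a screener knows what to do, and the defect is an imprecise summary. This stands as regards which text governs. It does not remove the problem, because Section 15 makes a specific statement about how a risk is controlled, and that statement is untrue for patients whom Section 5 admits.

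A second reply is that the two bronchodilator types are thin. Those patients have neither asthma nor wheeze, and nothing shows that they have reactive airway disease. This also stands: they are secondary, and the substance is active against any asthma.

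A third reply is that other safeguards limit the harm. Section 10.0 provides for a single 60-minute infusion with monitoring in the operating room and PACU. Section 15.0 has a plan to stop the drug and treat, puts severe reactions at 1% or less, says of patients with bronchospasm that "Bronchodilating agents are effective in treating these patients", and adds that "all possible medication reactions will be reported to the Anesthesia DSMB and MUSC IRB". This stands and keeps the point minor.

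A reader might infer that the conflict runs both ways, with Section 15 admitting a user of a non-prescribed inhaled bronchodilator whom Section 5 excludes. The documents do not support that. Section 15 also leaves out body weight, pregnancy, clotting deficiency and insulin-dependent diabetes, all of which Section 5 excludes. Its silence therefore makes nobody eligible.

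**Conclusion.** The inconsistency is real and minor. Both sentences are current protocol text, and nothing in either document reconciles them. If Section 5 is applied, three types of patient can be enrolled although Section 15 says they are excluded: chiefly quiescent asthma, and secondarily a prescribed but unused bronchodilator or a prescribed non-inhaled one. The conflict runs in one direction only.

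The conclusion rests on the literal wording and on Section 5 being the list that screeners use. The documents give neither the prevalence of these types nor a reaction rate specific to reactive airway disease, so no number of patients or events is estimated. A reader might also infer that unsuitable patients were enrolled, or that the broader rule was the one intended. The documents show neither. Randomisation, sample size and analysis are unaffected.

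**What to change.** Use one wording in both sections. Section 15's reason is pre-existing reactive airway disease, so the preferred change is to amend Section 5 to the union of the two existing rules and repeat it in Section 15:

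*Asthma, wheezing, prescribed bronchodilators, or using inhaled bronchodilators.*

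This goes no further than the two present rules together. The cost is a one-line edit in each section and a few more screen failures, number unknown.

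If the clinicians intend the narrower rule, keep Section 5 and correct Section 15 so that it claims no broader exclusion than is applied. That is a one-line edit with no added screen failures. Either way, Section 15's prior-reaction sentence can be matched to Section 5 in the same edit.

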6.0 Number of Subjects

Sample size: 70 subjects

First 20 subjects: We will initially randomize 5 patients to each dose group (placebo, 50, 100, and 150 mg/kg) to estimate the dose response curve and to identify the optimal dose. After enrollment of the first 20 patients, the study will undergo review by the study team and statistician.

- If the dose response curve is adequate and the optimal dose identified, 15 additional patients will be randomized to placebo and 15 to the optimal dose to estimate the difference in opioid consumption between patients on placebo vs. the optimal dose. (Total of 50 subjects with 20 from dose response curve and 30 to estimate the difference in opioid consumption.)
- If the dose response curve is not adequate after the initial 20 subjects 5 per each dose group, we will randomize and enroll an additional 5 patients to each dose group (placebo, 50, 100, and 150 mg/kg) to estimate the dose response curve and to identify the optimal dose. Once the optimal dose is identified with these initial 40 patients, 10 additional patients will be randomized to placebo and 10 to the optimal dose to estimate the difference in opioid consumption between patients on placebo vs. the optimal dose. (60 patients total with 40 to create the dose response curve and 20 more to estimate the difference in opioid consumption.)
- A sample size of 20 subjects per group (placebo and optimal dose) allows us to estimate a 95% confidence interval for the mean difference in opioid consumption with a width of ± 0.64 standard deviations from the mean. We will plan to consent 70 subjects to account for withdrawal but will complete the study once 50 or 60 subjects (based on the number of subjects required to create the dose response curve) have completed the protocol.

7.0 Setting

MUSC surgical clinics or preoperative anesthesia clinics

8.0 Recruitment Methods

- Potential subjects on the surgical schedule undergoing elective surgery of the spine involving 4 levels or less will be screened for eligibility.
- Information regarding the study will be presented to subject by a study team member in the surgical clinic or preoperative anesthesia clinic or in the preoperative period prior to sedation. On the day of surgery, subjects may then choose to provide written consent, decline to participate, or rescind their prior consent.

9.0 Consent Process

- Regardless of the preoperative location, the study team will present to the subject with risks and benefits of the study and the study medication (NAC). Subjects may provide written consent at that time or choose to consider the study until the day of surgery. Potential participants will be given time to read the consent and ask questions. Consent will be obtained from subjects by an IRB approved CITI certified study team member that has been trained on the protocol. Written consent will be completed once all questions are answered and exclusion and inclusion verified. Copies of all documents will be provided to the patients.

10.0 Study Design / Methods

Design: This prospective, double blinded clinical trial will randomize patient to receive placebo (0.45% NaCl or 0.9% NaCl) or NAC (50, 100, or 150 mg/kg). The randomization will be created by a statistician and shared with Investigational Drug Services (IDS) pharmacy prior to patient enrollment.

IDS pharmacy has planned to set up the study to be dispensed from the main OR pharmacy. IDS will prepare numbered kits containing NAC or placebo based on the randomization scheme. The kits will be stored in the OR pharmacy and dispensed based on the assigned subject number. This will allow enrollment any time of day that the OR pharmacy is open.

Groups: Patients will be randomized to receive NAC: 0 mg/kg (placebo; 0.45% NaCl or 0.9% NaCl), 50 mg/kg, 100 mg/kg, and 150 mg/kg (Max dose 15,000 mg). The maximum dose considered will be 150 mg/kg as this has been studied for safety in numerous patient populations including those with severe comorbidities. As NAC may be reconstituted in D5W or 0.45% NaCl, we will reconstitute all NAC doses in 250ml 0.45% NaCl or D5W. We will use 250ml 0.45% NaCl or 0.9% NaCl without NAC as our placebo.

Enrollment:

Following confirmation of informed written consent, patients will be assigned an enrollment number and randomized using the randomization, created by a statistician, to one of four IV NAC groups: 0 mg/kg (placebo; 0.45% NaCl or 0.9% NaCl), 50 mg/kg, 100 mg/kg, or 150 mg/kg. Patients will proceed to the operating room where they will receive general anesthesia for their planned, elective surgical procedure. Intraoperatively, the designated IV NAC or placebo infusion will be initiated and completed by a clinical care team member. Patients will only receive NAC once as a single dose that will run over 60

minutes. Patients will be monitored in the operating room while receiving NAC and in the PACU postoperatively consistent with our standard perioperative care at MUSC.

The recorded anesthesia stop will mark time zero. The primary end point will be 12-hour postoperative opioid consumption.

Patient and procedural characteristic will be recorded throughout the perioperative period. Demographic data (age, gender, race, weight, height, body mass index) and preoperative opioid consumption will be collected after completion of informed consent (yes or no; and consumption quantified if applicable). Surgical data (operative procedure and surgical duration) will be collected after surgery. Time of hospital discharge will be collected after the patient is discharged from the hospital.

Other exploratory outcomes will be collected as long as the patient is still in the hospital and able to self-report up to 48 hours post-operatively. Data will be collected from subject self-reporting their VAS score and using the electronic medical record. These data include intraoperative opioid consumption, postoperative anesthesia care unit (PACU) opioid consumption cumulative, non-opioid analgesic administration, postoperative opioid consumption up to 48 hours or discharge. VAS pain scores will be recorded pre-operatively, post operatively and at 24 hours unless discharged prior to 24 hours post operatively.

In order to identify the optimal IV NAC dose for perioperative opioid reduction and estimate the difference in opioid consumption between placebo and the selected optimal dose, the study will progress in two phases.

- In the first phase (20 subjects), we will attempt to identify the optimal dose. The optimal dose is defined as the dose or doses of NAC for which a $\geq 20\%$ reduction in opioid consumption relative to placebo is expected based on the dose response curve. If 20% reduction is not achieved, the optimal dose will be the maximum dose (150 mg/kg) administered during the study.
- In the second phase, after finding the optimal dose, 15 additional patients will be randomized to placebo and 15 to the optimal dose to estimate the difference in opioid consumption between patients on placebo vs. the optimal dose (30 subjects). A sample size of 20 subjects per group (5 from phase 1 and 15 from phase 2) allows us to estimate a 95% confidence interval for the mean difference in opioid consumption with a width of ± 0.64 standard deviations from the mean.
- If we are unable to create a dose response curve following the enrollment of the first 20 subject, an additional 20 subjects (5 per group) will be enrolled to create the dose response curve prior to starting the second phase.

Research procedures: The IV NAC dose [0 mg/kg (placebo; 0.45% NaCl or 0.9% NaCl), 50 mg/kg, 100 mg/kg, or 150 mg/kg] will be the only research procedure.

All other aspects of preoperative (e.g., clinic visits, labs, imaging) intraoperative (e.g., surgical procedures, anesthesia medications or procedures), and postoperative care (e.g., hospital admission and care, clinic follow-up, labs, imaging) will not be research procedures but consistent with planned patient care for a patient having elective spine surgery. The patient will be responsible for all charges related to the surgery and perioperative care excluding the NAC medication.

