An IND is not required for this study. First, NAC is FDA approved for IV administration. Next, the doses studied do not exceed the FDA approved doses. Further, this study does not and will not seek to change the FDA labeling. Last, NAC has an over 60-year history of efficacious and safe use. The history of NAC use at the proposed dosages does not suggest a substantial risk or harm to patients.

Pharmacy: NAC is currently stored in the MUSC OR and inpatient pharmacies. It is easily prepared by reconstituting in D5W or 0.45% NaCl. We will reconstitute in 250 ml of D5W or 0.45% NaCl, and 0.45% or 0.9% NaCl will also serve as our placebo. NAC is FDA approved and can currently be ordered by any physician for administration if indicated. Study related NAC will be ordered and administered perioperatively following enrollment. NAC is stable once prepared for 24 hours.

IDS pharmacy has planned to set up the study to be dispensed from the main OR pharmacy. IDS will prepare numbered kits containing NAC or placebo based on the randomization scheme. The kits will be stored in the OR pharmacy and dispensed based on the assigned subject number. This will allow enrollment any time of day that the OR pharmacy is open.

References

3. Radomska-Leśniewska DM SP. N-acetylcysteine as an anti-oxidant and anti-inflammatory drug and its some clinical applications. *Cent J Immunol*. 2012;37(1):57-66.

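### In a trial described as double blinded, NAC and placebo have different lists of permitted fluids, and no masking of the bag is described

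*Protocol*

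**What the plan says.** Section 10.0 of the protocol describes the trial as double blinded but does not list who is blinded. On the active arms, its Groups paragraph says "we will reconstitute all NAC doses in 250ml 0.45% NaCl or D5W". On the control arm it says "We will use 250ml 0.45% NaCl or 0.9% NaCl without NAC as our placebo". The pharmacy text in Section 18.0 gives the same two lists: "We will reconstitute in 250 ml of D5W or 0.45% NaCl, and 0.45% or 0.9% NaCl will also serve as our placebo". Section 3.0 and the research-procedures paragraph of Section 10.0 repeat the placebo fluids.

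The only concealment step described is at the pharmacy: "IDS will prepare numbered kits containing NAC or placebo based on the randomization scheme". Kits are dispensed by subject number. In the operating room, "the designated IV NAC or placebo infusion will be initiated and completed by a clinical care team member".

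On the outcome, Section 10.0 says "The primary end point will be 12-hour postoperative opioid consumption". The same section leaves anesthetic medication and postoperative care to usual practice, and no rule for opioid dosing is given. The SAP does not mention blinding.

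**The concern.** A double-blind comparison needs infusions that cannot be told apart. Here the stated rule itself lets the fluid differ by arm, which goes beyond a missing detail about labels. Each arm has one fluid that the other may not use, and nothing says when each fluid is chosen or that the choice must be matched across arms.

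Opioid consumption depends in part on what staff decide to give. If staff know the arm, their dosing can move with it, and the estimated difference between NAC and placebo would then mix the drug effect with that response.

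The design gives such an influence some leverage. Phase 1 selects the dose from 5 patients per group against a 20% reduction relative to placebo. The phase 1 patients in the placebo and selected-dose groups then count again in the final comparison of 20 per group (5 from phase 1 and 15 from phase 2). Any distortion in phase 1 would therefore carry forward.

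**Working it through.** **Step 1. The plan's own figure.** The documents give no figure for blinding. Their one sample-size figure is a 95% confidence interval of ±0.64 SD with 20 per group. It reproduces: t(0.975, 38 df) × √(2/20) = 2.0244 × 0.3162 = 0.640 SD. The present point does not depend on it.

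**Step 2. The permitted fluids side by side** (Sections 10.0 and 18.0, which agree).

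| Fluid, 250 ml | NAC 50, 100, 150 mg/kg | Placebo |
|---|---|---|
| 0.45% NaCl | permitted | permitted |
| D5W | permitted | not listed |
| 0.9% NaCl | not listed | permitted |

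One fluid is common and two are specific to an arm. An arm-specific fluid separates NAC from placebo. It does not separate the three NAC doses from one another.

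**Step 3. How many patients the fluid could identify.** Let p be the share of NAC bags made up in D5W and q the share of placebo bags that are 0.9% NaCl. The documents give neither, so every value below is an assumption. Assume also that staff can learn which fluid was used.

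- Phase 1 allocates 5 patients to each of four groups, so NAC to placebo is 3:1. The share of arm-specific bags is 0.75p + 0.25q.
- Phase 2 allocates 1:1. The share is 0.5p + 0.5q.
- For the remaining bags, all 0.45% NaCl, the best guess is the arm that supplies more of them. The share classified correctly is the arm-specific share plus the larger of the two remaining parts: in phase 1 the larger of 0.75(1 − p) and 0.25(1 − q), in phase 2 the larger of 0.5(1 − p) and 0.5(1 − q).

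| p | q | Arm-specific bags, phase 1 | Arm-specific bags, phase 2 | Correctly classified, phase 1 | Correctly classified, phase 2 |
|---|---|---|---|---|---|
| 0 | 0 | 0% | 0% | 75% | 50% |
| 0.25 | 0.25 | 25% | 25% | 81% | 62.5% |
| 0.5 | 0.5 | 50% | 50% | 87.5% | 75% |
| 1 | 0 | 75% | 50% | 100% | 100% |
| 0 | 1 | 25% | 50% | 100% | 100% |
| 1 | 1 | 100% | 100% | 100% | 100% |

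The first row is the benchmark: with the shared fluid throughout, the bag tells staff nothing beyond the allocation ratio.

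The rows with p = 1, q = 0 and p = 0, q = 1 show that one arm's habit is enough. If all NAC is in D5W and all placebo in 0.45% NaCl, then 0.45% NaCl also comes to mean placebo, and every patient is identifiable to anyone who knows the practice.

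**Step 4. From fluid to outcome.** For the fluid to influence the result, three links are needed: the fluid is visible on the bag, label or record; that knowledge reaches those who decide on opioids; and it changes what they give. The documents neither establish nor exclude any of them. They give no basis for a size of the last link, so none is calculated.

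**The case against.** The strongest reply is that the plan allows a fully matched trial. 0.45% NaCl is open to all four arms, the randomization is made by a statistician and shared with the pharmacy, and kits are numbered and dispensed by subject number. Details of labelling may sit in pharmacy documents that are not part of the protocol or SAP. This stands as far as it goes: unblinding is possible, not shown. It does not remove the point, because numbering a kit conceals the allocation before dispensing and says nothing about what can be read on the bag. Nor does the protocol require the shared fluid to be used.

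A reader might infer several stronger things that the documents do not support.

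- **That the arms do use different diluents.** The text gives overlapping lists, not a fixed fluid for each arm.
- **That patients' own pain reports would be affected.** The infusion runs during general anesthesia, so patients are not placed to see the bag.
- **That whoever hangs the bag decides the opioids in the outcome.** Time zero is the recorded anesthesia stop, and later opioids are given in PACU and on the ward. The information would have to travel by handover, by the record or through shared staff.
- **That dextrose biases the result.** A 250 ml D5W bag holds 250 × 5/100 = 12.5 g of dextrose, and no permitted placebo holds any. That is a second possible difference between arms, but nothing in the documents links it to opioid consumption.

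**Conclusion.** The concern holds as a weakness in the written safeguards. The permitted fluids are not matched across arms, one fluid on each list is exclusive to an arm, and no masking of bag, label or record is described. That much rests on the text alone and is firm.

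The extent is unknown. The share of patients identifiable as NAC or placebo runs from 0% to 100%, depending on fluid use by arm, which the documents do not give, and on whether staff can recognise the fluid. With an even split of fluids in each arm it would be 50%, and that split is an assumption. The effect on the estimated opioid difference cannot be sized from the documents.

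The finding does not show that the blind was broken or that the primary result is biased. It is a change that should be made because it is specific and cheap and protects an outcome that depends partly on staff decisions.

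**What to change.** Reconcile the fluid lists in Sections 3.0, 10.0 (including its research-procedures paragraph) and 18.0 so that all four arms use the same fluid. Which fluid that should be is for pharmacy and clinicians to decide. If supply forces a change, make it in all arms at the same time.

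State that the bag, its label and the entry in the administration record are identical across arms and masked, and name the roles that are blinded.

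If bags have already been dispensed, report the fluid used by arm, so that readers can see where the trial falls between 0% and 100%.

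The cost is a short protocol and pharmacy edit and less flexibility when the shared fluid is in short supply. The sample size and the ±0.64 SD precision do not change.
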